All subjects in the study will be randomized in a 1:1 ratio to receive either quadrivalent HPV (Types 6, 11, 16, 18) L1 VLP vaccine or placebo within investigative sites. Within the quadrivalent HPV vaccine group, subjects will be further randomized to receive 3 different lots of the vaccine in a 1:1:1 ratio. The actual lots received will differ between subjects enrolled in the consistency lot substudy and the remaining subjects in Protocol 015.

Subjects participating in the consistency lot substudy will be randomized in a 1:1:1:3 ratio to receive Consistency Lot 1 of quadrivalent HPV (Types 6, 11, 16, 18) L1 VLP vaccine, Consistency Lot 2 of quadrivalent HPV (Types 6, 11, 16, 18) L1 VLP vaccine, Consistency Lot 3 of quadrivalent HPV (Types 6, 11, 16, 18) L1 VLP vaccine, or placebo within investigative sites. This randomization will ensure a 1:1:1 allocation of subjects to the 3 quadrivalent HPV (Types 6, 11, 16, 18) L1 VLP vaccine consistency lots. It will also maintain a 1:1 ratio of subjects receiving quadrivalent HPV (Types 6, 11, 16, 18) L1 VLP vaccine (any lot) and placebo for the overall efficacy study.

For the non-consistency lot part of the study, the Interactive Voice Response System (IVRS) will assign a block of 18 allocation numbers to a study site upon allocation of the first subject at that site. Within the block of 18 numbers, 9 will be allocated to vaccine (3 to Lot No. VAI018I001, 3 to Lot No. VAI025T001, and 3 to Lot No. VAI025T002) and 9 to placebo in a 3:3 ratio in blocks of 6. The system will assign an additional block of allocation numbers to a study site once it has depleted its supply of numbers.

For the consistency lot substudy, the IVRS will assign a block of 18 allocation numbers to a study site upon allocation of the first subject at that site. Within the block of 18 numbers, 3 will be allocated to Consistency Lot 1, 3 to Consistency Lot 2, 3 to Consistency Lot 3, and 9 to placebo in a 1:1:1:3 ratio in blocks of 6. The system will assign an additional block of allocation numbers to a study site once it has depleted its supply of numbers.

For both parts of the study, case numbers will be assigned to the subjects sequentially at each study site beginning with the lowest number available at the site as subjects are enrolled in the study. This will retain the randomization and the treatment group ratio within study sites. Case numbers should not be reassigned for any reason.

C. Blinding/Unblinding

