follow-up. In this analysis, it will be assumed that subjects who are lost to follow-up prior to Month 7 (i.e., prior to completion of the vaccination series) would have been classified as cases at the same rate as the placebo recipients in the primary analysis regardless of treatment group. That is, an assumption of “no vaccine efficacy” will be made in subjects who do not complete the vaccination regimen. The incidence rate that will be assumed for subjects who are lost to follow-up at Month 7 or following Month 7 (i.e., after completion of the vaccination series) will depend on each subject’s treatment group. It will be assumed that vaccine recipients who complete the vaccination series and then drop out subsequently would have developed the endpoint of interest at the same rate as the vaccine recipients in the primary analysis (who will all have also completed the vaccination series). It will be assumed that placebo recipients who complete the vaccination series and then drop out subsequently would have developed the endpoint at the same rate as the placebo recipients in the primary analysis.

g. Interaction

Prior to conducting the formal statistical analyses described above, tests for study site by treatment group interaction will be performed. This section describes the general approach that will be taken for assessing the presence and nature of the interactions.

All interaction tests will be conducted at the $\alpha = 0.10$ level. If no statistically significant interaction is found, then the study sites will be pooled for the analysis. If a significant treatment-by-study center interaction is found, the nature of the interaction will be examined and the relevance of the interaction in the context of the planned analysis will be evaluated. If the interaction cannot be disregarded, certain study sites may be analyzed separately.

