A test for treatment-by-study center interaction will be conducted to evaluate whether or not the difference in proportions between 2 lots is consistent across study centers. Treatment-by-study center interaction will be tested separately for each pair of the 3 consistency lots and for each vaccine HPV type. An improved version (Mehrotra [4], Mehrotra & Chan [5]) of the Brown and Forsythe [6] testing procedure will be used.

The test statistic to be used is as follows:

$$F^* = \frac{\sum_{k=1}^K n_k (d_k - \bar{d})^2}{\sum_{k=1}^K \left(1 - \frac{n_k}{N}\right) n_k V_k}$$

D. Statistical Methods (Cont.)

where,

$$d_k = \hat{p}_{1k} - \hat{p}_{2k}$$

$$\bar{d} = \frac{\sum_{k=1}^K n_k d_k}{N}$$

$$n_k = \frac{2n_{1k}n_{2k}}{n_{1k} + n_{2k}}$$

$$V_k = \left(\frac{\hat{p}_{1k}(1-\hat{p}_{1k})}{n_{1k}-1} + \frac{\hat{p}_{2k}(1-\hat{p}_{2k})}{n_{2k}-1} \right)$$

and,

K = number of study centers

\hat{p}_{1k} = observed proportion with the response of interest in Group 1
at study center k

\hat{p}_{2k} = observed proportion with the response of interest in Group 2
at study center k

n_{1k} = sample size in Group 1 at study center k

n_{2k} = sample size in Group 2 at study center k

$$N = \sum_{k=1}^K n_{1k} + n_{2k} = \text{total sample size.}$$

The critical value that F^* will be compared to is $F_{0.90}(f_1, f_2)$, the 90th percentile of the central F distribution with f_1 and f_2 degrees of freedom. As shown by Mehrotra [4], appropriate values of f_1 and f_2 are given by:

D. Statistical Methods (Cont.)

$$f_1 = \frac{\left(\sum_{k=1}^K n_k V_k - \frac{\sum_{k=1}^K n_k^2 V_k}{N} \right)^2}{\sum_{k=1}^K (n_k V_k)^2 + \left(\frac{\sum_{k=1}^K n_k^2 V_k}{N} \right)^2 - 2 \frac{\sum_{k=1}^K n_k^3 V_k^2}{N}}$$

$$f_2 = \frac{\left[\sum_{k=1}^K \left(1 - \frac{n_k}{N} \right) n_k V_k \right]^2}{\sum_{k=1}^K \left(1 - \frac{n_k}{N} \right)^2 \left(\frac{(n_k V_k)^2}{n_k - 1} \right)}$$

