These interaction tests will be conducted at the $\alpha = 0.10$ significance level. If a statistically significant interaction is detected (p -value ≤ 0.10), the discussion of such an interaction will include an evaluation of its relevance in the context of the planned equivalence test. For example, the treatment effect differences will be estimated for each study center separately and will be displayed graphically. Observational and graphical assessment of the magnitude and nature of the interaction will be made in relationship to the prespecified margin for the equivalence tests (10 percentage points). The procedure to test for qualitative interaction proposed by Gail and Simon [7] will be used to characterize the observed interaction. This procedure will be adjusted for the equivalence margin (10 percentage points). If the interaction cannot be disregarded, certain study centers may be analyzed separately.

2) Interaction Assessment for Ration of GMTs

An ANOVA model will be used to evaluate whether or not the ratio of GMTs between 2 lots is consistent across study centers. In the ANOVA model, the natural log of the RIA titers will be the dependent variable and treatment group, study center and treatment-by-study center interaction will be the independent variables. The independent variables will be treated as fixed effects in the model.

D. Statistical Methods (Cont.)

These interaction tests will be conducted at the $\alpha = 0.10$ level. Regardless of whether or not a given interaction test is statistically significant, the treatment-by-study center interaction term will be included in the final ANOVA model. If a statistically significant interaction is detected, the discussion of such an interaction will include an evaluation of its relevance in the context of the planned test of equivalence. For example, the ratios of the GMTs between treatment groups will be estimated separately by study center and will be displayed graphically. Observational and graphical assessment of the magnitude and nature of the interaction will be made in relationship to the prespecified GMT ratio for the GMT comparison (0.5). The procedure to test for qualitative interaction proposed by Gail and Simon [7] will be used to characterize the observed interaction. This procedure will be adjusted for the equivalence margin (2-fold). If the interaction cannot be disregarded, certain study centers may be analyzed separately.

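### The response-rate interaction statistic divides harmonic-mean centre weights by the total sample of both lots, so a lot difference identical in every centre inflates F* and the test does not hold its 0.10 level

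*SAP*

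**What the plan says.** SAP section VII.D.2.e.1 sets up the test to "evaluate whether or not the difference in proportions between 2 lots is consistent across study centers", separately for each pair of lots and each HPV type. For center k, d_k is the difference in observed response proportions, and the weight n_k is 2·n_1k·n_2k/(n_1k + n_2k), the harmonic mean of the two lot sizes. The mean difference d-bar is Σn_k·d_k divided by N, and N is given as "N = \sum_{k=1}^K n_{1k} + n_{2k} = \text{total sample size". The same N appears in the denominator of F* and in both degrees-of-freedom formulas. F* is compared with "the 90th percentile of the central F distribution with f_1 and f_2 degrees of freedom", and the section states: "These interaction tests will be conducted at the $\alpha = 0.10$ significance level".

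After a significant result the plan calls for an evaluation of relevance against the 10-point margin, plots by center and a qualitative-interaction test. It then adds: "If the interaction cannot be disregarded, certain study centers may be analyzed separately".

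On allocation, section VII.B says: "This randomization will ensure a 1:1:1 allocation of subjects to the 3 quadrivalent HPV".

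**The concern.** The null hypothesis is that the lot difference is the same in every center. That common difference need not be zero. A valid statistic must therefore measure the spread of the d_k around their own weighted mean, which requires weights that sum to 1. Dividing harmonic-mean weights by the full two-lot sample does not give that.

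N is defined both in symbols and in words, so this is not a fault of text extraction. Elsewhere the plan normalises its center weights: W_i over ΣW_k in VII.D.2.b, and center size over total evaluable size in VII.D.2.d. Only this statistic does not.

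At stake is whether a significant interaction result means what the plan takes it to mean. A uniform lot difference could be read as inconsistency between centers.

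**Working it through.** **Inputs.** Evaluable subjects per lot: 500 × 0.82 × 0.85 = 348.5, stated as 348 (VII.A.2, HPV 16 and 18). Response rate 90% (VII.A.2). Margin 10 points. Lots 1:1:1 (VII.B). Interaction level 0.10. Centers are pooled when a lot has fewer than 5 subjects there (VII.D.2.f). The number of centers K is not given, so K is an assumption, varied from 4 to 60.

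**The plan's own figures.** Simulated power for the three pairwise equivalence tests is 98.2% at 348 per lot and 98.7% at 361, against the stated 98.3%. The surrounding inputs therefore reproduce. The only number attached to this statistic is its level, 0.10.

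**Step 1: the weights.** The harmonic mean never exceeds the ordinary mean, so n_k ≤ (n_1k + n_2k)/2, with equality for equal lots. Hence S = Σn_k is N/2 under 1:1 allocation and less otherwise. A difference of 5 points in every center gives d-bar = 2.5 points.

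**Step 2: the numerator.** Let D = Σn_k·d_k/S, the proper weighted mean. Then d-bar = D/2, and

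Σn_k(d_k − d-bar)² = Σn_k(d_k − D)² + S·D²/4.

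The last term comes from the common difference alone. For 94% v 86% it is 348 × 0.08²/4 = 0.557. With equal centers the denominator of F* is about (K − 0.5) × (0.94×0.06 + 0.86×0.14) = (K − 0.5) × 0.1768. The amount added to F* is therefore about 0.557/(3.5 × 0.1768) = 0.90 at K = 4, 0.557/(11.5 × 0.1768) = 0.27 at K = 12, and 0.557/(59.5 × 0.1768) = 0.05 at K = 60. The distortion grows with the square of the difference and shrinks with K.

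**Step 3: degrees of freedom.** With equal centers and equal variances, the printed f1 reduces to (K − c)²/(K + c² − 2c), where c = S/N.
- N = S (c = 1): (K − 1)²/(K − 1) = K − 1, as it should be.
- N as printed (c = 1/2): (K − 0.5)²/(K − 0.75), which is 20.25/4.25 = 4.76 at K = 5 (should be 4) and 90.25/9.25 = 9.76 at K = 10 (should be 9).

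The formulas therefore need N = Σn_k.

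**Step 4: rejection rates with no interaction.** Formulas as printed, 348 per lot, equal centers, rates symmetric about 90%, 20,000 simulated data sets per cell (simulation error at most about ±0.007):

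| Uniform difference | K=4 | K=8 | K=12 | K=20 | K=30 | K=60 |
|---|---|---|---|---|---|---|
| 0 points | 0.08 | 0.08 | 0.08 | 0.07 | 0.07 | 0.04 |
| 3 points | 0.11 | 0.10 | 0.09 | 0.08 | 0.07 | 0.05 |
| 5 points | 0.16 | 0.13 | 0.12 | 0.10 | 0.08 | 0.05 |
| 8 points | 0.36 | 0.24 | 0.20 | 0.15 | 0.13 | 0.07 |
| 10 points | 0.60 | 0.39 | 0.30 | 0.22 | 0.17 | 0.09 |

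With N = Σn_k every cell lies between about 0.04 and 0.10 and hardly depends on the difference: about 0.10 at K = 4, 0.08 at K = 20 and 0.04 to 0.05 at K = 60.

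**Sensitivity.** The placing of the rates matters. At K = 5 and 10 points, 95% v 85% gives 0.52 and 90% v 80% gives 0.36. Unequal center sizes change little (0.35 in the latter case).

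**The case against.** The formula slip itself cannot be defended, but its consequences are easily overstated.

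- **A reader might infer that the test signals interaction whenever lots differ uniformly.** It does not. At the planning assumption of equal lots it is slightly conservative, and up to 3 points it stays near or below nominal. With the center differences free of noise, F* stays below its critical value in every case examined: 0.76 against 1.96 for K = 5, 90% v 80%. This stands.
- **The large rates arise where consistency mostly fails anyway.** At a true 8-point difference, the 90% interval for one pair lies within ±10 points in only about 23% of trials (unstratified approximation). Among those, the false-signal rate is 0.14 at K = 4 and 0.11 to 0.12 at K = 8 to 12, against roughly 0.09 to 0.10 with the right N. This also stands: where equivalence is met, the excess is a few percentage points.
- **K may be large.** With at least 5 per lot after pooling, up to 69 strata are possible (348/5 = 69.6), and at K = 60 the rate stays below 0.10 even at 10 points. This is fair, but the plan does not fix K, and small K is equally open under its pooling rule.
- **A reader might infer that the primary result is compromised.** The documents do not support that. Lot consistency rests on the p-values of the stratified equivalence tests (VII.D.2.a and VII.D.2.b), which do not use F*. Separate analysis of centers is discretionary and follows further evaluation.
- **A reader might extend the point to efficacy or GMTs.** The efficacy interaction test in VII.D.1.g is an exact test of homogeneity of relative risks, and the GMT test is an ANOVA term. Neither uses this N. The number of interaction tests run at 0.10 is likewise a separate matter, unchanged by correcting N.

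**Conclusion.** The definition of N is wrong as written. Under 1:1 lots it halves d-bar, distorts the denominator of F*, f1 and f2, and makes the statistic respond to a uniform lot difference that belongs to its own null hypothesis. The stated 0.10 level then fails by an amount that rises with that difference and falls with the number of centers: negligible at 0 to 3 points, and as tabulated above for 5 to 10 points. The direction follows from algebra alone. The sizes rest on an assumed K, 348 per lot and rates symmetric about 90%. The practical impact is limited, because this is a preliminary check in a substudy whose success is separate from that of the efficacy study, and it does not enter the equivalence tests.

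**What to change.** In SAP section VII.D.2.e.1, define N as Σn_k over centers wherever it appears (d-bar, the denominator of F*, f1 and f2), and delete the description of N as the total sample size. Check the analysis program against the corrected formula: with equal centers and equal variances f1 must equal K − 1, and a difference identical in every center must give F* = 0. The change costs one line of text. It needs no further data and leaves the sample size, the 0.10 level and the equivalence tests as they are.

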house blinded” studies, i.e., blinding for study participants, investigators, and internal Merck personnel. The in-house unblinded database will be “frozen” in order to ensure that analyses of data in response to regulatory queries will be performed on the same data as were used for that submission.

E. Description of Protocol Violations

The per-protocol analyses of efficacy and immunogenicity will exclude data according to the following rules:

1. Violations With Respect to the Vaccination Regimen or Sample Collection Regimen

- a. Subjects who received any of their 3 vaccinations outside of the day ranges specified in Section VIII.A will be excluded from the immunogenicity analyses only. Subjects who did not receive all 3 vaccinations within a year will be excluded from the efficacy analysis.
- b. Subjects who received the incorrect clinical material or an incorrect dose of the correct clinical material at any of the 3 vaccination visits will be excluded.
- c. Incorrectly randomized subjects will be excluded.

2. Inclusion/Exclusion Criteria Violations

- a. Subjects who are younger than 16 or who are older than 26 years of age will be included.
- b. Subjects who have engaged in sexual intercourse within 48 hours prior to a scheduled visit that includes a pelvic examination will be included.
- c. Subjects who become pregnant prior to Month 6 and subsequently choose to continue the pregnancy (i.e., not terminate the pregnancy) will be included in the efficacy analyses as long as they received all 3 vaccinations within 1 year. These subjects will likely be excluded from the immunogenicity analyses as they most likely missed vaccinations due to the pregnancy.
- d. Subjects who have a lifetime history of more than 4 male or female sexual partners will be included.

E. Description of Protocol Violations (Cont.)

- e. Subjects who are concurrently enrolled in clinical studies of investigational agents or studies involving collection of cervical specimens may or may not be included. These subjects will be judged on a case-by-case basis by the Clinical Monitor while the Clinical Monitor is still blinded and without knowledge of each individual's case status.
- f. Subjects with a history of any prior abnormal Pap test showing SIL, ASC-US, ASC-H, or biopsy showing CIN will be included in the analyses of HPV type-specific endpoints as long as they are negative for the appropriate HPV types by an MRL assay. These subjects will be excluded from analyses involving HPV types for which MRL has no available type-specific assay.
- g. Subjects with a history of genital warts or genital warts present at baseline will be included in the analyses if they were enrolled in the study.
- h. Subjects with any known or suspected immune disorders may or may not be included. These subjects will be judged on a case-by-case basis by the Clinical Monitor while the Clinical Monitor is still blinded to each subject's treatment allocation and case status.
- i. Subjects who are immunocompromised or have been diagnosed as having HIV infection will be excluded.

3. Concomitant/Prior Therapy Violations

- a. Subjects who have received any immune globulin (including RhoGAMTM) or blood derived products at any time through Month 7 of the study will be excluded.
- b. Subjects receiving any immunosuppressives will be excluded with the exception of subjects using topical or inhaled steroids.
- c. Subjects who receive any nonstudy inactivated vaccine within 14 days of a study vaccine will be excluded as well as subjects who receive any nonstudy live virus vaccine within 21 days before or 14 days after a study vaccine.
- d. Subjects who have had prior vaccination with an HPV vaccine will be excluded.

IX. PRESENTATION AND FORMAT OF RESULTS

A. Outline of Results Section

The following is an outline of the anticipated sections that will appear in the “Results” section of the CSR.

Results

- A. Study Subjects and Data Sets Analyzed
- B. Efficacy Evaluation and Results
- C. Immunogenicity Evaluation and Results
- D. Safety Evaluations

B. Format of Data Within Tables

1. Decimals

All means, standard errors, percentages, and confidence intervals will be reported to 1 decimal place.

2. Rounding

Means, standard errors, percentages, and confidence intervals endpoints will be rounded up to the next decimal place if the second decimal place is ≥ 5 and down to the next decimal place if the second decimal place is < 5 .

C. Notation and Ordering of Treatment Groups

1. Efficacy and Safety

Group 1: Quadrivalent HPV (Types 6, 11, 16, 18) L1 VLP Vaccine	Group 2: Placebo
--	---------------------

2. Immunogenicity

